1. INTRODUCTION

1.1 Specific Aims

It is hypothesized that blood flow restriction (BFR) therapy can help stimulate muscular development while recovering from surgery, producing a more rapid increase in function and an expedited return to playing sports.

Our primary objective is to determine the effect BFR exercises on the functional outcomes of patients recovering from ACL reconstruction, compared to that of a control group using a standard rehabilitation protocol. The secondary objective is to determine if any adverse effects or complications are associated with BFR therapy.

1.2 Hypotheses

It is hypothesized that patients undergoing BFR will show significantly improved outcome measurements throughout rehabilitation after ACL reconstruction.

	Rehabilitation with BFR	Standard Rehabilitation without BFR
KOOS	Better	Worse
IKDC	Better	Worse
VAS	Better	Worse
Limb Symmetry Index (LSI)	Better	Worse
Thigh circumference	Better	Worse
Return to sport	Better	Worse

Null Hypothesis: There is no statistically significant difference in the functional outcomes of patients using a standard ACL rehabilitation protocol versus a standard ACL rehabilitation protocol augmented with BFR therapy.

1.3 Background and Significance

Recovery from anterior cruciate ligament (ACL) reconstruction involves early physical therapy to promote muscular development. Traditional training regimens are based on the concept that muscle growth is induced with high resistance exercises of at least 65-70% of 1-repetition maximum [1,4]. Achieving a high resistance level can be challenging in the early post-surgical patient who may be limited by pain, muscle atrophy, diminished proprioception, and psychological factors. Increasing evidence has suggested that Blood Flow Restriction (BFR) in resistance training, while transmitting a decreased load (25-50% of 1-repetition maximum) across the surgical site, may provide an additional benefit of inducing muscular development similar to that of high intensity exercises [2].

Augmenting exercises with BFR involves an external pressure cuff applied to the proximal portion of the extremity, which is inflated to a pressure that restricts venous outflow while allowing arterial inflow to continue. This creates a pooling of oxygen poor blood that causes a buildup of lactic acid and protons, which stimulates ILGF-1, and other factors that lead to the release of human-growth hormone (HGH), and muscle hypertrophy. This allows patients to gain the hypertrophic effect of high resistance training, though at a lower and safer resistance level. Studies suggest that BFR stimulates muscular development through an increase in metabolic stress, muscle fiber recruitment, cell swelling, and protein synthesis [5-8].

Despite numerous basic science studies supporting the use of BFR in general strength development, and muscular development in deconditioned patient populations, few articles have assessed the role of BFR therapy in postoperative rehabilitation in athletes. When utilizing BFR in isolation without strength training for patients after ACL reconstruction, an early study [7] found a decrease in disuse quad atrophy based on MRI cross-section area (CSA), but these results could not be reproduced in a later study [2] with similar methodology. In another study of patients following ACL reconstruction, significantly greater increases in muscle strength and CSA were seen after 16 weeks in patients performing therapy exercises with BFR when compared to a non-BFR control group [3]. The purpose of this investigation is to assess the functional outcomes of patients using BFR therapy, compared to a control group, following ACL reconstruction.

1.4 Preliminary Studies

No preliminary studies have been performed. The Principal Investigator is a board-certified, fellowship trained Orthopedic Sports Medicine Surgeon.

2. STUDY DESIGN AND SUBJECT SELECTION

2.1 Study Type

This will be a single-center randomized control trial. Patients will be recruited, consented, enrolled, and randomized before their ACL reconstruction surgery

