The Effect of Blood Flow Restriction Therapy Following Anterior Cruciate Ligament Reconstruction

[name]

Inova Medical Group – Sports Medicine
[name]
10/13/2020

Table of Contents

SECTION	PAGE
1. INTRODUCTION	1
2. STUDY DESIGN AND SUBJECT SELECTION	3
3. STUDY METHODS AND PROCEDURES	4
4. STATISTICAL CONSIDERATIONS AND DATA ANALYSIS	8
5. HUMAN SUBJECTS PROTECTION	9
6. SUBJECT COMPENSATION	9
7. ADVERSE EVENT REPORTING	10
8. FUNDING	10
9. CONFLICTS OF INTEREST	10
10. FACILITIES AND EQUIPMENT	10
11. OUTSIDE CONSULTANTS/COLLABORATORS	10
12. CONTRACTUAL AGREEMENTS	10
13. REFERENCES	11

ABSTRACT

Title: The Effect of Blood Flow Restriction Therapy on Outcomes Following Anterior Cruciate Ligament Reconstruction

Short Title: Effect of BFR on ACL Reconstruction

Rationale: To investigate the effect of Blood Flow Restriction (BFR) exercises on the recovery process following an Anterior Cruciate Ligament (ACL) reconstruction.

Objectives: The main objective is to determine the impact of BFR therapy, in comparison to a standard rehabilitation protocol, on the functional outcomes of patients recovering from ACL reconstruction. The secondary objective is to determine if there are any adverse effects associated with BFR exercises.

Study Type: Prospective Randomized Control Trial (Level 1)

Study Design: Prospective Randomized Control Trial

Study Methodology:

Prospective data will be collected on 150 patients total, randomly divided into two groups based on the physical therapy regimen: (1) standard ACL rehabilitation (control group), and (2) standard ACL rehabilitation plus BFR therapy (BFR group). Patients in the BFR group will begin BFR therapy post-operative week 2, which will consist of the standard ACL rehabilitation exercises augmented with a pressure cuff during the session.

Inclusion criteria will consist of patients 13-55 years undergoing ACL reconstruction. Exclusion criteria include concomitant ligament reconstruction or concurrent procedures that require delayed weight bearing such as High Tibial Osteotomy (HTO), microfracture, etc. Additional exclusion criteria include history of DVT/PE, immunocompromising conditions, history of coagulation disorders or current use of anticoagulants, and pregnancy.

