2.8 Exclusion Criteria

Patients with a diagnosed ACL reconstruction that chose not to undergo reconstruction

1. Concomitant ligament reconstruction
2. Concurrent procedures that require delayed weight bearing (ie: HTO, multiligament reconstruction, microfracture, etc)
3. History of DVT/PE
4. Immunocompromising conditions (ie: Rheumatoid arthritis, chronic steroid use, etc.)
5. History of coagulation disorders or current use of anticoagulants
6. Completion of physical therapy at a location not affiliated with the study
7. Pregnancy

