3. STUDY METHODS AND PROCEDURES

3.1 Study Treatment/Intervention

Patients assigned to the intervention group will undergo BFR exercises in addition to the standard rehabilitation protocol. BFR therapy will be administered at an INOVA physical therapy location by a certified physical therapist that is trained in BFR modalities. Therapists will follow a standardized ACL rehabilitation protocol (see appendix), which consists of 2-3 therapy sessions per week following surgery. BFR exercises will begin after the surgical incision has healed and post-operative swelling is minimized. This generally occurs two weeks post-operatively.

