3.3 Randomization

Upon enrollment in the study, before their surgery, patients will be randomly assigned to the treatment group (75 subjects) or control group (75 subjects) using a random number generator.

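### Randomisation takes place before surgery, about two weeks or more before the arms differ, so operative choices and exclusions made at surgery can depend on the arm

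*Combined protocol and SAP*

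**What the plan says.** Section 2.1 sets the order of events: "Patients will be recruited, consented, enrolled, and randomized before their ACL reconstruction surgery". Section 3.3 agrees: "Upon enrollment in the study, before their surgery, patients will be randomly assigned to the treatment group (75 subjects"), with the same number assigned to control. The method given there is a computer or similar source of random numbers. It says nothing about who holds the assignment or when it is disclosed.

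The stated treatment difference comes later. The Abstract (Study Methodology) says "Patients in the BFR group will begin BFR therapy post-operative week 2". Section 3.1 makes the start conditional: "BFR exercises will begin after the surgical incision has healed and post-operative swelling is minimized", and adds "This generally occurs two weeks post-operatively". Section 3.2 gives controls the standard rehabilitation without BFR.

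Exclusion 2 in section 2.8 reads "Concurrent procedures that require delayed weight bearing (ie: HTO, multiligament reconstruction, microfracture, etc"). Section 3.6 repeats this exclusion as a note within its list of intraoperative data. That list also holds graft type, graft fixation, meniscal and chondral findings, meniscectomy, meniscal repair, chondroplasty and microfracture. Section 3.5 shows that the participating surgeons are study personnel, in the section on who may obtain consent.

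**The concern.** Assignment precedes the first stated treatment difference by the wait for surgery plus about two weeks. Two things can happen in that interval that would be harmless if the arm did not yet exist.

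First, operative decisions become post-randomisation events. If the surgeon knows the arm, the choice between meniscectomy and repair, the handling of a chondral lesion, or the graft (if chosen after assignment) can differ between arms. These choices can plausibly affect KOOS, IKDC, the hop-based limb symmetry index and return to sport, all primary outcomes in section 3.4.1. A difference between arms would then not be due to BFR alone.

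Second, eligibility can be settled after the patient has been counted in an arm. Keeping a patient who meets exclusion 2 at surgery dilutes the contrast. Removing the patient loses numbers and, if the decision can depend on the arm, threatens comparability. Section 4 does not say which is to be done.

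**Working it through.** **1. The sequence, from the documents.**

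| Event | Time | Source |
|---|---|---|
| Consent, enrolment, randomisation | Before surgery | 2.1, 3.3 |
| Baseline KOOS, IKDC, VAS, thigh circumference | Before surgery; order relative to randomisation not stated | 3.6 |
| Meniscal and chondral procedures; exclusion 2 may be triggered, for example by microfracture | At surgery | 2.8, 3.6 |
| Graft type and fixation | Recorded as intraoperative data; time of choice not stated | 3.6 |
| BFR begins in one arm | About two weeks after surgery | Abstract, 3.1 |

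The documents describe no concealment of the arm, no withholding of it until after surgery, no masking of the surgeon, and no stratification by graft or meniscal procedure.

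**2. The plan's own figure.** Section 4.1 gives 150 patients, 80% power and alpha 0.05; the Abstract makes tests two-sided. The figure cannot be reproduced, because no standard deviation, target difference or loss rate is given. Working backwards with the normal approximation for two means, 75 per arm detects (1.960 + 0.842) × √(2/75) = 0.457 SD with 80% power. The steps below use the corresponding noncentrality, 1.960 + 0.842 = 2.80, and power = Φ(noncentrality − 1.960).

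**3. Patients who never reach the point where the arms differ.** The documents give no rate, so the fraction f is assumed to be 5%, 10% or 15%.

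- *Kept as assigned, with outcomes measured and no BFR effect:* the mean effect is multiplied by (1 − f), so the noncentrality is 2.80 × (1 − f).
- *Dropped equally from both arms:* the effect is unchanged but n per arm becomes 75 × (1 − f), so the noncentrality is 2.80 × √(1 − f).

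| f (assumed) | Kept: noncentrality | Kept: power | Dropped: n per arm | Dropped: power |
|---|---|---|---|---|
| 5% | 2.66 | 75.9% | 71.25 | 78.0% |
| 10% | 2.52 | 71.3% | 67.5 | 75.7% |
| 15% | 2.38 | 66.3% | 63.75 | 73.3% |

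**4. Scale of bias if exclusion depends on the arm.** Every input here is assumed. Let a fraction p = 20% of patients have a prognosis worse by g SD, and let a fraction e of one arm only, all from that group, be excluded. That arm's mean shifts by g × [p − (p − e)/(1 − e)].

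- e = 5%, g = 0.5: 0.5 × (0.20 − 0.15/0.95) = 0.02 SD
- e = 15%, g = 1.0: 0.20 − 0.05/0.85 = 0.14 SD

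This shows only that the shift could range from negligible to a noticeable part of 0.457 SD. It does not estimate what will happen.

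**The case against.** The best defence is that randomising before surgery and analysing as assigned is a legitimate design, and that the real gap is concealment. That is partly right. Withholding the arm from the surgical team until after surgery would deal with arm-aware operative choices, and it belongs in the fix as the minimum. On its own, however, it leaves patients who become ineligible at surgery holding an assignment.

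Several stronger readings are tempting but go beyond the text:

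- *That graft is chosen in the operating room.* Section 3.6 records graft among intraoperative data but does not say when it is chosen. It is exposed only if chosen after assignment. Weight bearing appears there only through the exclusion note, not as a recorded choice.
- *That exclusion 2 is always settled at surgery.* Section 4.3.1 has the radiology report reviewed for exclusion criteria, so some cases can be found earlier. Microfracture and similar intraoperative decisions remain, at an unknown rate.
- *That the power loss measures biased surgery.* It measures only dilution or lost numbers. Section 4.1 also says 150 already allows for loss and early withdrawal. Without a figure, that allowance can be neither credited nor dismissed.
- *That later randomisation stops patients withdrawing once they learn their arm.* The cuff is visible, so such withdrawal is only postponed.
- *That the condition for starting BFR should become an entry criterion.* Section 3.1 says when BFR begins, not who is eligible. It gives no threshold for swelling, and using it as an entry criterion would change the population.

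Finally, the rehabilitation appendix is not in the supplied text. Identical care before BFR starts is inferred from the main text.

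**Conclusion.** The point holds as a design weakness that can be corrected cheaply. As written, the plan assigns the arm before operative decisions that can affect both eligibility and prognosis, with no stated safeguard and no stated reason for assigning so early. A reader might infer that surgeons will know the arm and act on it. The documents do not say so; they only fail to prevent it.

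The size of any bias is unknown. The power figures (about 66% to 76% if patients are kept, 73% to 78% if dropped equally) rest on assumed rates of 5% to 15% and on taking the plan's unreproduced 80% at face value. The case for change rests on the sequence of events, not on those figures.

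**What to change.** Keep consent, enrolment and all baseline measures before surgery. Amend sections 2.1 and 3.3 along these lines: *Consented patients are randomised after surgery, once the operative record confirms that exclusion criterion 2 is not met and before BFR could start in either arm. The 150 patients (75 per arm) are counted from randomisation.*

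If randomisation must stay before surgery, the minimum is to conceal the assignment from the surgical team and the patient and to open it at that same post-operative point. Section 4 should then also say how patients found ineligible before opening are counted and analysed.

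Leave the BFR start condition in section 3.1 as a matter of delivery; do not turn it into an eligibility rule.

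The cost is a protocol amendment and slightly more than 150 patients consented in order to randomise 150. There is also some scheduling work. Sections 3.1 and 3.2 have therapy 2-3 times a week following surgery, so sessions may already be under way. BFR needs a trained therapist and on-site equipment, so each patient must be booked where either arm can be delivered once the assignment is known. Section 3.6 lists no outcome assessment between baseline and 3 months, so the protocol must also name the contact at which the assignment is issued.

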2.2 Setting/Location

Surgery will be performed at an Inova facility. Physical therapy will be performed at an INOVA-affiliated physical therapy facility. Patients will be followed throughout their recovery in an outpatient setting at the Inova Orthopedics and Sports Medicine offices located [name].

2.3 Duration of Study

The study will encompass an enrollment period of 150 patients undergoing ACL reconstruction, as well as an additional 2 year of follow up after the final patient undergoes surgery.

2.4 Number of Subjects

The goal is to include 150 subjects in the study, which will be divided into 75 patients in the treatment group and 75 patients in the control group.

2.5 Study Population

2.5.1 Gender of Subjects

Subjects of all genders will be included in this study.

2.5.2 Age of Subjects

Patients 13-55 years old will be eligible for inclusion.

2.5.3 Racial and Ethnic Origin

Patients of all races and ethnicities will be open to inclusion.

2.5.4 Vulnerable Populations

Consent for enrollment and outcome measures may be translated for non-English speakers as needed. Pregnant women will be excluded from the study. Minors will be enrolled in the study with consent obtained from their guardians.

2.6 Recruitment

Recruitment will include all patients that meet the inclusion criteria who choose to undergo ACL reconstruction with an INOVA sports medicine fellowship-trained orthopedic surgeon.

2.7 Inclusion Criteria

1. Age 13-55 years at the time of surgery
2. ACL reconstruction
3. Using an Inova affiliated physical therapy practice for rehabilitation

2.8 Exclusion Criteria

Patients with a diagnosed ACL reconstruction that chose not to undergo reconstruction

1. Concomitant ligament reconstruction
2. Concurrent procedures that require delayed weight bearing (ie: HTO, multiligament reconstruction, microfracture, etc)
3. History of DVT/PE
4. Immunocompromising conditions (ie: Rheumatoid arthritis, chronic steroid use, etc.)
5. History of coagulation disorders or current use of anticoagulants
6. Completion of physical therapy at a location not affiliated with the study
7. Pregnancy

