3.6 Data Collection

The following data will be recorded:

Demographics:

- Gender
- Age at time of surgery
- BMI at time of surgery
- Sports participation (if applicable):
 - Type of sport
 - ie: football, soccer, baseball, track, etc.
 - Level of competition
 - High school
 - Collegiate

- Professional
 - Recreational
- Prior knee injuries:
 - Eg. ipsilateral/contralateral ACL tears, meniscal injuries, chondral injury
- Smoking status
 - Non-smoker
 - Former smoker
 - Smoker (number of packs per day)
- Diabetes

Injury Data:

- Laterality of injury
 - Left
 - Right
- Date of injury
- Time from injury to surgery
- Mechanism of injury:
 - Contact
 - Non-contact (ie: twisting)
- Concomitant ligament injury observed on MRI:
 - Ligament
 - Medial Collateral Ligament (MCL)
 - Lateral Collateral Ligament and/or Posterolateral corner (LCL/PLC)
 - Posterior Cruciate Ligament (PCL)
 - Severity of injury
 - Grade 1: (minor sprain) high signal is seen medial (superficial) to the ligament, which looks normal
 - Grade 2: (severe sprain or partial tear) high signal is seen medial to the ligament, with high signal or partial disruption of the ligament
 - Grade 3: complete disruption of the ligament
 - Note: Concomitant ligament injury *requiring reconstruction* is an exclusion criteria

Intraoperative Data:

- Type of ACL graft:
 - Bone-patellar tendon bone (BTB) autograft
 - Hamstring tendon (HS) autograft
 - Allograft
- ACL graft fixation (interference screws, suspensory fixation)
- Concomitant injuries observed intraoperatively
 - Meniscal tear
 - Medial vs. Lateral
 - Type of tear (longitudinal, radial, degenerative, bucket-handle)
 - Chondral injury
 - Location
 - Medial compartment
 - Lateral compartment
 - Patellofemoral joint
 - Severity (Outerbridge Classification)
 - Grade 0: normal
 - Grade I: cartilage with softening and swelling

- Grade II: partial-thickness defect with fissures on the surface that do not reach subchondral bone or exceed 1.5 cm in diameter
 - Grade III: fissuring to the level of subchondral bone in an area with a diameter more than 1.5 cm
 - Grade IV: exposed subchondral bone
- Concomitant procedures performed:
 - Meniscectomy
 - Partial vs. Complete
 - Medial vs. Lateral
 - Meniscal repair
 - Chondroplasty
 - Microfracture
 - Note: Concomitant procedure requiring delayed weightbearing is an exclusion criteria

Outcome Data:

- Validated patient reported outcomes:
 - Surveys:
 - Knee Injury and Osteoarthritis Outcome Score (KOOS)

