4.3 Data Storage

4.3.1 Data Management

All records related to a subject's involvement in this research study will be stored in a locked file cabinet on the second floor of the Inova Orthopaedic and Sports Medicine Group. The subject's identity of these records will be indicated by a case number rather than by name, and the information linking these case numbers with their identity will be kept separate from the research records. Only the researchers listed on the first page of this form and their staff will have access to a subject's research records.

Data will be collected in a standardized fashion by the physicians and office staff. No publication or reports will contain any identifying information about individual participants. PI, co-investigators, and research staff will review medical records, private office charts, and obtain new questionnaires from patients. The radiology report will be reviewed for exclusion criteria. Only IRB-approved study members will have access to the data and study materials. Epic clinical information databases will be reviewed for information gathered from clinic visits and/or surgery.

Data accuracy and protocol compliance will be assessed during standard Quality Control operations, to include compliance checks and regular data verification. Protocol deviations will be reported to the IRB as policy. Noncompliance will be reported to the IRB as standard.

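### Exclusion 6 is worded by where therapy is completed, so applied literally it removes patients after randomisation, and no analysis population is stated

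*Combined protocol and SAP*

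**What the plan says.** **Timing.** Section 2.1: "Patients will be recruited, consented, enrolled, and randomized before their ACL reconstruction surgery". Section 3.3: "Upon enrollment in the study, before their surgery, patients will be randomly assigned". Sections 3.1 and 3.2 place the study therapy of both arms after surgery, at 2-3 sessions per week.

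**Therapy site.** Exclusion 6 in 2.8 reads "Completion of physical therapy at a location not affiliated with the study". Inclusion 3 in 2.7 covers similar ground: "Using an Inova affiliated physical therapy practice for rehabilitation". Section 2.6 ties the inclusion criteria to recruitment: "Recruitment will include all patients that meet the inclusion criteria".

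**Findings at surgery.** Exclusion 2 in 2.8 reads "Concurrent procedures that require delayed weight bearing (ie: HTO, multiligament reconstruction, microfracture, etc". Under Intraoperative Data, 3.6 lists microfracture among the procedures to be recorded and adds "Note: Concomitant procedure requiring delayed weightbearing is an exclusion criteria". Section 4.3.1 says "The radiology report will be reviewed for exclusion criteria". It also describes review of medical records, office charts and the electronic record of surgery, together with compliance checks.

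**Analysis.** The Abstract names repeated-measures ANOVA. Section 4.1 says that 150 patients allow for loss to follow-up and withdrawal, without a rate. Section 4.2 gives descriptive statistics and measures of association. Section 4.3.1 sends protocol deviations to the IRB. None of these defines an analysis population or says how a randomised patient who later meets an exclusion is analysed.

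**The concern.** An exclusion that can be applied after allocation gives an analyst textual authority to drop randomised patients, possibly once outcomes are known. That is harmless only if the reason for dropping is unrelated to arm and outcome. A change of therapy site may well be related to both. No blinding is described, the arms receive visibly different therapy, and patients may move because of slow progress, discomfort or satisfaction. Removing them would then compare two groups that randomisation no longer makes alike, and the error could favour either arm.

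Exclusion 2 raises a smaller version of the same question. A procedure decided in theatre also comes after allocation, and a preoperative radiology report cannot show it. If theatre decisions are independent of allocation, removing these patients costs numbers and introduces no bias.

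**Working it through.** **1. Order of events.** Enrolment and randomisation (2.1, 3.3), then surgery, then therapy (3.1, 3.2). Where post-operative therapy is completed is therefore settled after allocation. Inclusion 3, by contrast, can be judged at enrolment from the patient's plan.

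**2. The plan's own figure.** Section 4.1 gives 80% power, alpha 0.05 and 150 patients, but no SD, target difference or loss rate, so 150 cannot be reproduced. Solving backwards with a two-sided t test, 75 per arm with no loss has 80% power for a difference of 0.46 SD. That value is used below.

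**3. Bias if exclusion 6 is applied literally.** All rates are assumed. Let p1 and p0 be the proportions removed in the two arms, and g the amount in SD by which removed patients do worse than those retained. There is no true effect.
- Shift = (p1 − p0) × g, towards the arm with more removals.
- n per arm = 75 × (1 − p); SE = √(1/n1 + 1/n0).
- Type I error from the noncentral t distribution with noncentrality shift/SE, two-sided 0.05.

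Example: 20% v 5% with g = 1.0 gives n = 60 and 71.25, shift = 0.15 × 1.0 = 0.15 SD, SE = √(1/60 + 1/71.25) = 0.175, and type I error 13.6%.

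| Removed | Gap (SD) | Shift (SD) | Type I error |
|---|---|---|---|
| 5% v 5% | 0.5 or 1.0 | 0 | 5.0% |
| 8% v 5% | 0.5 / 1.0 | 0.015 / 0.030 | 5.1% / 5.4% |
| 15% v 5% | 0.5 / 1.0 | 0.05 / 0.10 | 6.0% / 8.9% |
| 20% v 5% | 0.5 / 1.0 | 0.075 / 0.15 | 7.1% / 13.6% |

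**4. Analysing as assigned.** This protects only as far as outcomes are obtained. If a share f of the would-be-removed patients supply outcomes, each arm's analysed mean is off by g × [p − pf/(1 − p + pf)], and the shift is the difference between arms. For 20% v 5%, g = 1.0 and f = 0.5: (0.20 − 0.10/0.90) − (0.05 − 0.025/0.975) = 0.0889 − 0.0244 = 0.0645 SD. Over the range from 8% v 5% with g = 0.5 to 20% v 5% with g = 1.0:
- half obtained: 0.007-0.065 SD, type I error 5.0-6.7%;
- three quarters obtained: 0.003-0.030 SD, 5.0-5.4%;
- all obtained: 0 SD, 5.0%.

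**5. Dilution from keeping them.** If a share m of the BFR arm moves off-site and keeps a fraction k of the effect, the detectable difference becomes 0.46 × [1 − m(1 − k)]. With 75 per arm:
- k = 0.5: power 78% (m = 5%) to 74% (m = 15%);
- k = 0: 76% to 66%.

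**6. Exclusion 2 met at surgery, independent of arm.** Bias is nil. With no loss allowance, removing 10% of both arms leaves 67.5 per arm and 75.7% power. Keeping them gives 0.46 × 0.95 and 75.9% power if those in the BFR arm get half the effect, or 0.46 × 0.90 and 71.3% if they get none. Neither choice is better in every case.

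**The case against.** The strongest reply is that exclusion 6 is a screening item. It sits in a list of screening items, inclusion 3 says nearly the same thing in a form that can be judged at enrolment, and 2.6 ties recruitment to the inclusion criteria. That reading is reasonable, so it would be too strong to say that the criterion can be met only after randomisation. It does not close the gap. If the item merely repeats inclusion 3, it is redundant and rewording costs nothing. The plan would still not say how a randomised patient who later changes site is analysed.

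A reader might infer that the protocol instructs staff to drop randomised patients. It does not: no section orders removal, and 2.2 plans follow-up at the Inova office with no condition on therapy site, which makes silent loss of outcomes less likely. That answers the follow-up question but leaves open who is analysed.

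A reader might also infer that the radiology report is the only eligibility check. It is the only source expressly tied to the exclusion criteria, but 4.3.1 also describes chart review, electronic surgical records and compliance checks.

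Finally, a reader might infer that exclusion 2 biases the comparison, or that every patient meeting it at surgery must be kept. No section suggests that allocation influences theatre decisions, though none rules it out. If it does not, keeping or excluding is a trade-off in power.

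**Conclusion.** The point holds, and should be fixed. Exclusion 6 as worded permits removal after randomisation on a criterion that may be related to arm and outcome, and no statement of the analysis population prevents it.

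The size cannot be derived from the documents. The 5.1-13.6% range rests on assumed removal rates, an assumed difference between arms and an assumed outcome gap. The upper figure needs the most extreme combination considered, and equal rates with the same gap give no shift. The model is a single comparison of means, not the repeated-measures ANOVA or the return-to-sport date. Confidence is medium, because the intended meaning of exclusion 6 is uncertain.

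The exclusion 2 matter is secondary: a missing pre-specification that, if independent of arm, costs only numbers.

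**What to change.** **Section 2.8.** Delete exclusion 6, or reword it as the intended therapy site at enrolment, in line with inclusion 3. Treat later off-site therapy as non-adherence.

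**Section 4.2.** State that randomised patients who change therapy site are followed for the scheduled outcomes and analysed in their assigned arm. Report their number, and the share with outcomes obtained, by arm.

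**Secondary, also in 4.2.** Pre-specify one of two rules for patients first found at surgery to meet exclusion 2: keep them as assigned, or exclude them by a decision on surgical findings made blind to arm. Report the numbers by arm under either rule.

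**Cost.** A short amendment covering follow-up and analysis only; treatment is unchanged. Keeping patients who change site dilutes the effect, by the amounts in step 5 of the working. The therapist-completed BFR survey (3.6) would not be available for off-site sessions. The protection depends on these patients still attending the Inova office, which 2.2 already plans. If patients meeting exclusion 2 at surgery are kept, some early hop tests may be missing.
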